10.3.1.2. Statistical Evaluation of Safety

Safety parameters that will be assessed include safety laboratory parameters, vital signs, ECG parameters, injection-site reactions, and hypoglycemia. The parameters will be listed and summarized using standard descriptive statistics.

Laboratory measurements will be summarized with respect to observed values and change from baseline by treatment group at each time point using descriptive statistics. In addition, all clinical chemistry, hematology, and urinalysis data outside the reference ranges will be tabulated by parameter and treatment group.

Vital signs will be summarized with respect to observed values and change from baseline (Day 1, Predose) by treatment at each time point using descriptive statistics. For change from baseline values, a mixed-model repeated-measure model with treatment, time (of measurement), and treatment-by-time interaction as fixed effects, patient as random effect, and baseline as covariate will be used to determine the effects of LY3298176.

Electrocardiogram parameters, including the pulse rate, QT interval, RR interval, and QTc using Fridericia's formula (QTcF), QRS interval duration, and heart rate, will be summarized. The number and percentage of patients with a maximum increase from baseline in QTcF will be summarized for each treatment group according to the following categories: >30 milliseconds and >60 milliseconds. In addition, the number and percentage of patients with QTcF postdose values according to the following categories: >450 milliseconds, >480 milliseconds, and >500 milliseconds, will be summarized by treatment group. Exploratory analyses may be performed to determine the effects of LY3298176 concentration-response analysis of QTcF.

Additional analysis will be performed, if warranted, upon review of the data.

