Appendix 4. Clinically Significant Adverse Effects

The table below summarizes the type and severity of symptoms, clinical signs, and clinical laboratory findings that may qualify as a clinically significant event. These are intended as a guideline to the investigator(s), not as a set of absolute criteria. The underlying principle is to define a level of moderate to severe abnormality in safety findings that could cause harm to health and would preclude further dosing of a patient/subject who experiences this effect. Safety parameters not included in this table may be interpreted in a similar fashion according to investigator judgment.

Clinically Significant Adverse Effects

Parameter	CSE level
Symptoms	
Severe hypoglycemia	One episode of severe hypoglycemia defined as low blood glucose with mental status impairment severe enough to require third-party assistance
Dizziness/hypotension	Orthostatic CNS symptoms (dizziness, confusion) that are not vasovagal responses to provocative stimuli (for example, phlebotomy, nausea, bowel or bladder function), and are associated with orthostatic SBP decrease >20 mm Hg or DBP decrease >10 mm Hg or heart rate >105 bpm, for >3 hours
Sensorium	Disorientation to time, place, or identity. Any abnormal ideation
Mood	Feelings of grief or loss that interfere with study procedures or activities of daily living; any suicidal ideation
Headache/pain	Any focal or generalized head pain that disrupts normal activities and is not responsive to medical therapies
Pruritus	Generalized itching for more than 24 hours that is unresponsive to oral antihistamine
Signs	
Systolic blood pressure	>30 mm Hg increase from baseline values and an absolute level >190 mm Hg
Diastolic blood pressure	>20 mm Hg increase from baseline values and an absolute level >115 mm Hg
Heart rate	Resting (sitting or recumbent) HR >120 bpm
Cardiac rhythm	Any rhythm other than sinus rhythm, mild sinus bradycardia, or mild sinus tachycardia
QTc	>500 milliseconds or >60 milliseconds increase from baseline value
QRS morphology	Significant prolongation of QRS interval or new onset of bundle branch block
Tremor	Readily visible tremor during normal movement deemed unrelated to hypoglycemia
Reflexes	New onset of clonic reflexes
Clinical Laboratory	Confirmed by repeat measurements within 48 hours
Hemoglobin	Absolute value <10 g/dL and >2 g/dL reduction from baseline
Neutropenia	Absolute neutrophils <1,500/ μ L and >1,000 μ L decrease from baseline

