3. INTRODUCTION

This SAP has been developed after review of the Clinical Study Protocol (final version dated 24 August 2017).

This SAP describes the planned analysis of the safety, tolerability, pharmacokinetic (PK) and pharmacodynamic (PD) data from this study. A detailed description of the planned TFLs to be presented in the clinical study report (CSR) is provided in the accompanying TFL shell document.

The intent of this document is to provide guidance for the statistical analyses of PK and PD data. In general, the analyses are based on information from the protocol, unless they have been modified by agreement between Eli Lilly and Company and Covance Early Clinical (EC) Biometrics. A limited amount of information concerning this study (e.g., objectives, study design) is given to help the reader's interpretation. This SAP must be signed off prior to first patient administration for this study. When the SAP and TFL shells are agreed upon and finalized, they will serve as the template for this study's CSR.

This SAP supersedes the statistical considerations identified in the protocol; where considerations are substantially different, they will be so identified. If additional analyses are required to supplement the planned analyses described in this SAP, they may be performed and will be identified in the CSR. Any substantial deviations from this SAP will be agreed upon between Eli Lilly and Company and Covance EC Biometrics and identified in the CSR. Any minor deviations from the TFLs may not be documented in the CSR.

This SAP is written with consideration of the recommendations outlined in the International Council on Harmonisation (ICH) E9 Guideline entitled Guidance for Industry: Statistical Principles for Clinical Trials¹ and the ICH E3 Guideline entitled Guidance for Industry: Structure and Content of Clinical Study Reports².

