9. STATISTICAL METHODOLOGY

9.1 General

Data listings will be provided for all data that is databased. Summary statistics and statistical analysis will only be presented for data where detailed in this SAP. For continuous data, summary statistics will include the arithmetic mean, arithmetic standard deviation (SD), median, min, max and N; for log-normal data (e.g. the PK parameters: AUCs and C_{max}) the geometric mean and geometric coefficient of variation (CV%) will also be presented. For categorical data, frequency count and percentages will be presented. Data listings will be provided for all patients up to the point of withdrawal, with any patients excluded from the relevant population highlighted. Summary statistics and statistical analyses will generally only be performed for patients included in the relevant analysis population. For the calculation of summary statistics and statistical analysis, unrounded data will be used.

Mean change from baseline is the mean of all individual patients' change from baseline values. Each individual change from baseline will be calculated by subtracting the individual patient's baseline value from the value at the timepoint. The individual patient's change from baseline values will be used to calculate the mean change from baseline using a SAS procedure such as Proc Univariate.

Data analysis will be performed using SAS[®] Version 9.4 or greater.

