9.5.3 Clinical laboratory parameters

All clinical chemistry and hematology data will be summarized by treatment regimen and parameter together with changes from baseline, where baseline is defined as Day -1, and listed. Urinalysis data will be listed. Additionally clinical chemistry, hematology, and urinalysis data outside the reference ranges will be listed.

Values for any clinical chemistry, hematology, and urinalysis values outside the reference ranges will be flagged on the individual patient data listings.

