9.5.5 Electrocardiogram (ECG)

The ECG data will be obtained directly from the 12-lead ECG traces. These data include the PR, QT, QTcB intervals, QRS duration and heart rate, where QTcB is the QT interval corrected using Bazett's formula. In addition, QTcF (the QT interval corrected using Fridericia's formula) will be calculated as follows:

$$QTcF = \frac{QT}{\sqrt[3]{(60/HR)}}$$

The ECG data will be summarized by treatment regimen together with changes from baseline, where baseline is defined as the mean of all measurements on Day 1 predose of the treatment period. Figures of mean ECG data and mean changes from baseline will be presented by treatment regimen.

A plasma LY3298176 concentration-QT analysis will be performed to assess the changes from baseline (Day 1 predose) and placebo in the (double delta) QTcF interval relative to plasma LY3298176 concentrations across all active treatments. The change from baseline adjustment will be based on individual subject's Day 1 predose value, and the change from placebo adjustment will be based on the mean of time-matched placebo values.

Further details on how these will be calculated:

- Calculate the arithmetic mean of the triplicate QTcF for each subject at each timepoint and use this in all subsequent calculations below.
- Calculate the change from baseline at each timepoint for each individual subject who received LY3298176.
- Calculate the mean change from baseline across all the placebo subjects at each timepoint.

- For each subject that received LY3298176 at each corresponding timepoint subtract the mean placebo change from their own individual change from baseline.
- BLQ LY3298176 concentration data will be imputed to 50% of the LLOQ for the purposes of the analysis.

The analysis will be performed by plotting double delta QTcF against LY3298176 concentrations, including all post Day 1 dosing timepoints.

A mixed effects analysis model will be performed on the double delta QTcF values and will include LY3298176 concentration as a covariate and subject as a random effect. The results of the model and associated 90% CI will be fitted on the plot and the p-value for the slope reported. Estimated double delta QTcF and 90% CI at the geometric mean C_{max} will also be presented.

Additional analysis to evaluate effects of AE (such as gastrointestinal or hypoglycemia events) QTcF may be performed if deemed necessary.

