11. CHANGES FROM THE PROTOCOL SPECIFIED STATISTICAL ANALYSES

There were no changes from the protocol specified statistical analyses.

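### The SAP omits the protocol's QTcF category counts and by-group table of out-of-range laboratory results, yet states that no planned analysis changed

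*Protocol*

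**What the plan says.** **Protocol 10.3.1.2** makes three unconditional commitments.

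- For change in QTcF: "The number and percentage of patients with a maximum increase from baseline in QTcF will be summarized for each treatment group", with the categories ">30 milliseconds and >60 milliseconds".
- For absolute postdose QTcF: number and percentage of patients per treatment group above 450, 480 and 500 ms.
- For laboratory safety: out-of-range chemistry, hematology and urinalysis results set out in a table by analyte and treatment group.

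**SAP 9.5.5** says "The ECG data will be summarized by treatment regimen together with changes from baseline". It adds figures of means and a model of placebo-corrected QTcF change against drug concentration. No QTcF threshold appears there or elsewhere in the SAP.

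**SAP 9.5.3** summarizes chemistry and hematology with changes from baseline, and lists urinalysis. For abnormal results it says only that "data outside the reference ranges will be listed", with flags in the patient listings.

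Three general statements govern how the two documents fit together:

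- SAP Section 3: "This SAP supersedes the statistical considerations identified in the protocol". The same sentence promises that substantial differences will be identified.
- SAP 9.1: "Summary statistics and statistical analysis will only be presented for data where detailed in this SAP".
- SAP Section 11: "There were no changes from the protocol specified statistical analyses".

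**The concern.** Safety and tolerability is the primary objective, and counts of patients crossing QTcF thresholds are part of the safety output that the protocol promised. A programming team works from the SAP. If the SAP is silent, outranks the protocol, and says that nothing changed, the tables can drop out without anyone having decided to remove them.

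At stake is the completeness of the final safety report, and a reader's ability to see per regimen how many patients passed each QTcF threshold and how abnormal laboratory results were spread across groups. Data collection is not affected.

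**Working it through.** The plan states no figure for this point, so the check is a comparison of texts, followed by short arithmetic on what the planned summaries can and cannot show.

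**1. Side by side**

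| Output | Protocol 10.3.1.2 | SAP 9.5.3 and 9.5.5 |
|---|---|---|
| QTcF increase categories, patients per group | 2 (>30, >60 ms) | 0 |
| Absolute QTcF categories, patients per group | 3 (>450, >480, >500 ms) | 0 |
| Out-of-range laboratory table by analyte and group | 1 | 0 (listing and flags) |
| Concentration-QTcF analysis | optional | firm commitment |
| Differences declared in SAP Section 11 | – | 0 |

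In total, 2 + 3 = 5 QTcF categories and 1 laboratory table are in the protocol and absent from the SAP. The last analysis in the table moved the other way, from optional to planned, also without declaration.

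**2. Versions.** SAP Section 3 says it was written from the protocol of 24 August 2017. The summary of Amendment (a) lists changes only to Section 7.3 and Appendix 8, both on blinding. Nothing in it suggests that 10.3.1.2 changed, so a version difference does not explain the gap.

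**3. What the planned ECG summaries give.** SAP 9.1 defines a continuous summary as mean, SD, median, minimum, maximum and N. Applied to QTcF at each time point, the maximum shows whether at least one patient crossed a threshold at that time. It does not give the count.

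Inputs: planned group sizes are 12, 16 and 12 on active drug and 3 + 3 + 3 = 9 on pooled placebo, and 12 + 16 + 12 + 9 = 49, matching the planned enrollment. Take the regimen with n = 16 and assume that all 16 have an ECG.

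- *One time point.* Suppose the maximum increase is above 30 ms and the median is at or below 30 ms. With 16 values, a median at or below 30 ms means that at least 8 values are at or below 30 ms. The number above 30 ms is therefore between 1 and 8: 1/16 = 6.25% to 8/16 = 50%. The mean and SD narrow this but do not in general fix it.
- *Two time points.* Suppose exactly one patient is above 30 ms at each. If it is the same patient, the protocol's count is 1/16 = 6.25%. If they are different patients, it is 2/16 = 12.5%. Summaries by time point cannot tell these apart, because the protocol's statistic uses each patient's maximum over all postdose times.

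**4. Laboratory results.** A listing with flags holds every abnormal value but does not set the groups side by side by analyte. For urinalysis the SAP plans no summary at all.

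**The case against.** The case on the other side has real weight.

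- **Extremes stay visible.** A reader might infer that one large QTcF increase would disappear into a group mean. The documents do not support that: SAP 9.1 includes the maximum in every continuous summary, so an increase above 60 ms or a value above 500 ms would show by regimen. This stands. What is missing is the count, not the signal.
- **Individual data stay available.** SAP 9.1 provides listings of all databased data, and SAP 9.5.5 plots individual QTcF changes on active drug against concentration. With 9 to 16 patients per group, counts could be made by hand. This also stands; no data disappear.
- **The SAP does not forbid the tables.** A reader might infer that SAP 9.1 prohibits them. ECG and laboratory data are detailed in the SAP, and Section 3 lets additional analyses be performed and identified in the report. So the SAP is silent rather than prohibitive. But an optional allowance does not carry forward a firm commitment.
- **It may be an oversight.** SAP Section 3 also says that analyses generally follow the protocol unless changed by agreement, and Section 11 reports no change. The tables may never have been meant to go. If so, the remedy is the same: write them in.
- **The table shells were not available.** They may contain these outputs. If they do, the defect is confined to the SAP wording.
- **The dosing rules are not affected.** Protocol Appendix 4 gives a QTc of ">500 milliseconds or >60 milliseconds increase from baseline value" as a level that may qualify as a clinically significant event, and such events enter the criteria in Protocol 7.4.1. A reader might infer that the missing table weakens those criteria. It does not: Appendix 4 describes itself as guidance, the investigator determines such events, and the criteria operate while dosing is under way. An end-of-study table plays no part in them.
- **The laboratory gap is smaller.** The protocol does not specify counts or percentages for that table, and the SAP still lists abnormal values separately.

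**Conclusion.** The point holds as a mismatch between protocol and SAP in planned safety outputs. Five QTcF categories and one laboratory table promised in Protocol 10.3.1.2 are not in the SAP, and the statement in SAP Section 11 is wrong as it stands. Followed literally, the SAP would report extremes and individual values, but not the per-regimen number and percentage of patients based on each patient's maximum QTcF, nor the by-group table of abnormal laboratory results.

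This rests on two assumptions: that ECG summaries are produced by time point with the statistics in SAP 9.1, and that the table shells do not supply the missing outputs. It should be corrected because it concerns the primary objective and costs little. It does not show that a safety signal would go unseen, that data would be missing, or that protection of patients during dosing is reduced.

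**What to change.** 1. **SAP 9.5.5.** Add the number and percentage of patients per regimen in the five QTcF categories. Use each patient's maximum postdose triplicate mean and, for the increases, the Day 1 predose baseline already defined there. State how single ECGs are handled: Protocol 9.4.3 has them recorded locally at follow-up or early termination, while the schedule footnote names Day 85 or early termination, so the status of the Day 64 ECG should be stated too. Say whether unscheduled ECGs count.
2. **SAP 9.5.3.** Add a table of out-of-range chemistry, hematology and urinalysis results by analyte and regimen, and define its cells, for example patients with at least one postdose value below or above range.
3. **If either output was dropped on purpose,** declare and justify this in SAP Section 11. In any case, correct the present statement there and record that the concentration-QTcF analysis became a firm commitment.
4. **Table shells.** Check that they match.

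The cost is two standard descriptive tables and a few lines of SAP text, from data already scheduled for collection.

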10.3.2. Pharmacokinetic Analyses

10.3.2.1. Pharmacokinetic Parameter Estimation

Pharmacokinetic parameter estimates for LY3298176 will be calculated by standard noncompartmental methods of analysis.

The primary parameters for analysis will be C_{max} , AUC, and T_{max} of LY3298176. Other noncompartmental parameters, such as half-life, apparent clearance, and apparent volume of distribution may be reported.

Model-based analysis will be performed combined with data from other studies. LY3298176 concentration data will be analyzed using a population PK approach via nonlinear mixed-effects modeling with the NONMEM software (NONMEM, Dublin, Ireland). Additionally, the effect of intrinsic and extrinsic patient factors such as age, weight, sex, and renal function on PK may be examined as needed.

10.3.2.2. Pharmacokinetic Statistical Inference

PK dose proportionality may be assessed in an exploratory manner in model-based analysis.

The parameter T_{max} of LY3298176 will be analyzed using a nonparametric method.

PK parameters will be summarized using descriptive statistics by dosing regimen.

10.3.3. Pharmacodynamic Analyses

10.3.3.1. Pharmacodynamic Parameter Estimation

The ability of LY3298176 to reduce fasting or dynamic glucose and the effects on insulin will be assessed. Such effects will be explored for different treatment regimens of LY3298176.

The AUC(0-2h) for glucose and insulin during an OGTT will be calculated using the trapezoidal rule. The AUC(0-2h) as well as other derived parameters or observed concentration at specific time points for each patient on the study day will also be baseline-adjusted. The concentrations on Day -1 will be used as baseline.

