- m Patients will be required to fast for at least 8 hours before each blood sample is drawn.
- n These tests will be performed at the local laboratory.
- o These tests will be performed per investigator's discretion.
- p Procedures may be repeated throughout the study as deemed necessary by the investigator.
- q Patients may be required to remain at the CRU longer than the planned discharging day at the investigator's discretion to assure patients' safety or to provide additional safety monitoring.
- r IMP will be administered after an overnight fast of at least 8 hours. IMP must be administered at least 6 days after the previous dose.

- s Assessments of injection-site reactions will be included in the medical assessments.
- t Weight will be measured in a consistent way per Section 9.4.2.1, always predose.
- u OGTT (serum glucose and insulin) sampling schedule: Pre-glucose dose (75 g) and 0.5, 1, 1.5, and 2 hours post glucose dose. Patients should consume the glucose load within 5 minutes after an overnight fast of at least 10 hours.
- v Only insulin and glucagon will be measured at 24 hours postdose on Day 51. All other time points include fasting glucose.
- w Meal intake and subjective rating of appetite sensation will be evaluated before and 4 to 5 hours after standardized lunch and dinner meals on Days -1, 2, and 51. The standardized lunch and dinner meals will be provided at least 4 hours after the previous meal or the ingestion of glucose in the OGTT.
- x Lipid panel includes high-density lipoprotein cholesterol, low-density lipoprotein cholesterol, total cholesterol, and triglycerides. Triglyceride and total cholesterol concentrations in the safety panel will not be required on the days that the lipid panel is performed.
- y Exploratory storage samples may be assayed for biomarkers like adiponectin, cortisol, and bone biomarkers. Refer to Section 9.6.2 for details.

3. Introduction

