9.4 Pharmacodynamic Assessment

9.4.1 Pharmacodynamic Analysis

The ability of LY3298176 to reduce fasting or dynamic glucose and the effects on insulin will be assessed. Such effects will be explored for different treatment regimens of LY3298176.

The following data will be summarized by treatment regimen and day, and listed:

- Fasting glucose concentrations
- Glucose concentrations and AUC(0-2h) during OGTT
- Insulin concentrations and AUC(0-2h) during OGTT
- Lipid panel (including high-density lipoprotein cholesterol, low-density lipoprotein cholesterol, total cholesterol, and triglycerides)
- Adiponectin concentrations (if available)
- Blood urea nitrogen concentrations
- Cortisol concentrations (if available)

- HbA1c concentrations
- 7-point glucose profile
- Markers of bone metabolism (if available)
- Meal intake and subjective rating of appetite sensation

The AUC(0-2h) for glucose and insulin during an OGTT will be calculated using the trapezoidal rule. The AUC(0-2h) as well as other derived parameters or observed concentration at specific timepoints for each patient on the study day will also be baseline-adjusted. The concentrations on Day 1, predose will be used as baseline.

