9.4.2 Pharmacodynamic Statistical Methodology

Statistical inference on PD parameters (fasting blood glucose, OGTT glucose, and insulin) will be based on the patients who are included in the PD population. PD parameters may be transformed before statistical analyses, if deemed necessary.

The observed results, as well as change from baseline, will be analyzed by treatment regimen, using mixed-effects models to evaluate treatment effects, as well as treatment comparisons. The model will include treatment regimen actually received, as a fixed effect and the patient as a random effect. For repeated measured parameters, day and treatment regimen-by-day interaction terms will be included in the model. Baseline (Day -1) values, as well as other influencing variables, may be used as covariates. An unstructured covariance structure will be applied. If the model fails to converge, alternative structures shall be examined using Akaike's criteria. The main comparisons will be between each LY3298176-treated group and placebo group. Least-squares means as well as 95% CIs will be reported.

Example SAS code for repeated measures analysis:

```
proc mixed data=pd;
  class subject trtreg day;
  model chg = base trtreg day trtreg*day / residual ddfm=kr;
  repeated day / subject=subject type=un;
  lsmeans trtreg / alpha=0.05 cl pdiff;
  ods output lsmeans=lsm;
  ods output diffs=diff;
run;
```

where 'chg' is the change from baseline, 'base' is the baseline value, and 'trtreg' is the treatment regimen.

Example SAS code for mixed-effects analysis:

```
proc mixed data=pd;
  class subject trtreg;
  model pd = trtreg / residual ddfm=kr;
  random subject;
  lsmeans trtreg / alpha=0.05 cl pdiff;
  ods output lsmeans=lsm;
  ods output diffs=diff;
run;
```

where 'trtreg' is the treatment regimen.

The individual observed and mean (SD) time profile of the postdose PD parameters will be plotted by treatment regimen. Additional exploratory analyses of PD parameters may be performed to understand dose response using relevant model considering titration scheme, as deemed appropriate.

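### Total AUC(0-2h) is the only derived OGTT measure specified, and by itself it cannot separate a lower fasting level from a smaller post-load glucose excursion or a changed insulin response

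*Protocol*

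**What the plan says.** Protocol 10.3.3.1 gives the aim as "The ability of LY3298176 to reduce fasting or dynamic glucose and the effects on insulin will be assessed". For the OGTT it specifies one derived quantity: "The AUC(0-2h) for glucose and insulin during an OGTT will be calculated using the trapezoidal rule". This AUC, other derived parameters that are not defined, and concentrations at given times "for each patient on the study day will also be baseline-adjusted".

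SAP 9.4.1 lists "Glucose concentrations and AUC(0-2h) during OGTT" and the matching insulin outputs, summarised by regimen and day. SAP 9.4.2 includes OGTT glucose and insulin among the parameters for inference.

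Footnote u of the Schedule of Activities (Protocol Section 2) sets the sampling: "Pre-glucose dose (75 g) and 0.5, 1, 1.5, and 2 hours post glucose dose". Appendix 7 counts 10 OGTT samples per patient, that is two five-point tests, each with its own pre-load sample.

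The baseline is described in three ways:

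- Protocol 10.3.3.1: "The concentrations on Day -1 will be used as baseline".
- SAP 9.4.1: "The concentrations on Day 1, predose will be used as baseline".
- SAP 9.4.2: "Baseline (Day -1) values, as well as other influencing variables, may be used as covariates".

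The schedules place the pre-treatment OGTT on Day -1 and none on Day 1. SAP Section 11 nevertheless declares no changes from the protocol analyses.

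**The concern.** Neither document subtracts the same-day pre-load value from the OGTT area or adjusts the OGTT comparison for it. Fasting plasma glucose is already the secondary PD endpoint (Protocol Section 4) and has its own inference. What the OGTT can add is the response to the glucose load, and total AUC mixes that response with the fasting level.

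The same applies to insulin. Protocol 9.6.1.1 says the OGTT is meant to inform disposition index and insulin sensitivity, but neither document gives a formula. Total insulin AUC moves with fasting insulin as well as with the response above it.

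At stake is how an exploratory result is interpreted: whether a regimen changed the excursion or the insulin response, or lowered the whole curve.

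**Working it through.** The plan states no figure for the AUC effect, so there is none to reproduce.

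**Inputs.** The sampling times are 0, 0.5, 1, 1.5 and 2 h (footnote u). The glucose curves below are assumptions, because the documents give no OGTT values.

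**Weights.** The trapezoidal rule gives 0.25, 0.5, 0.5, 0.5 and 0.25 h, which sum to 2.0 h. Writing G0 for the same-day pre-load value:

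- Total AUC = 0.25·G0 + 0.5·(G0.5 + G1 + G1.5) + 0.25·G2
- Incremental AUC = total AUC − 2·G0
- Change in total AUC = 2 × change in G0 + change in incremental AUC

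The last line holds for any curve. The net effect of a fasting change depends on how much of it carries over to the post-load samples. If a fraction c carries over, total AUC falls by 0.25 + 1.75c per unit.

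**Assumed curve.** Take 160, 240, 290, 290, 270 mg/dL. Total AUC = 40 + 120 + 145 + 145 + 67.5 = 517.5 mg.h/dL. Incremental AUC = 517.5 − 320 = 197.5 mg.h/dL.

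| Pattern | Change in total AUC (mg.h/dL) | Change in incremental AUC (mg.h/dL) |
|---|---|---|
| All five samples fall by 10 mg/dL (c = 1) | −20 | 0 |
| Pre-load falls by 10, post-load by 5 (c = 0.5) | −11.25 | +8.75 |
| Only pre-load falls by 10 (c = 0) | −2.5 | +17.5 |
| Whole curve falls by 10/160 | −32.3 | −12.3 |
| Only post-load samples fall by 10 | −17.5 | −17.5 |

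One total can come from different patterns. A parallel fall of 10 mg/dL gives −20. A fall of 20/1.75 = 11.4 mg/dL in the post-load samples alone also gives −20. In the first case the excursion is unchanged; in the second it is 20 mg.h/dL smaller.

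**Size under a parallel shift.** On this curve, falls of 20, 50 and 80 mg/dL lower total AUC by 40, 100 and 160 mg.h/dL (7.7%, 19.3% and 30.9% of 517.5). Incremental AUC stays at 197.5. Two other assumed curves behave the same way:

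- 170, 260, 310, 320, 300: total 562.5, incremental 222.5.
- 150, 230, 270, 260, 230: total 475, incremental 175.

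On these, falls of 20 to 60 mg/dL lower total AUC by 40 to 120 mg.h/dL, from 40/562.5 = 7.1% to 120/475 = 25.3%.

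**Does the SAP baseline remove the mixing?** Suppose SAP 9.4.1 means subtracting 2 h × Day 1 predose glucose, taken as 160. After a parallel fall of 50 mg/dL, total AUC is 417.5. The change is (417.5 − 320) − (517.5 − 320) = −100, so the fasting shift remains in full. A pre-treatment constant cannot remove it.

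**Noise.** The incremental weights are −1.75, 0.5, 0.5, 0.5 and 0.25. Assume independent error with equal variance at each sample. The error variance is then 3.875 units, against 0.875 for total AUC, so the error SD is √(3.875/0.875) = 2.1 times as large. This covers within-test error only, not variation between patients.

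**The case against.** Total AUC is a legitimate measure of exposure after the load. Post-load samples carry 1.75/2.0 = 87.5% of its weight, and under a parallel shift post-load glucose really is lower. SAP 9.4.1 also reports fasting glucose and OGTT concentrations, and SAP 9.4.2 plots individual and mean profiles, so a reader could see a parallel shift. Incremental AUC has its own ambiguity: it rises by 1.75 per unit when only the pre-load sample falls. It is also noisier, and only 9 placebo patients are planned (3 per cohort). All of this stands, and it is why the incremental measure should supplement total AUC and not replace it.

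It does not answer the core point. Seeing both parts on a plot is not a prespecified estimate of the excursion against placebo, and the time-point concentrations carry the same fasting shift.

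A reader might go further and infer that total AUC always falls by 2 per unit fall in fasting glucose, so that a purely fasting effect would be reported as an effect on dynamic glucose. The documents do not support this. The factor is 2 only when the excursion is unchanged; it is 0.25 if the pre-load sample alone falls. No sentence labels AUC as the dynamic measure, defines dynamic as the excursion above pre-load, or commits to such a claim.

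**Conclusion.** The point holds as a limit on what the planned OGTT summary can show. Total AUC(0-2h) alone does not identify whether the fasting level, the excursion or both have changed, and the same is true of insulin. The decomposition is exact. The net size is conditional: a 10 mg/dL fall in pre-load glucose goes with a fall in total AUC of 2.5 mg.h/dL if nothing carries over to later samples, and 20 if the excursion is unchanged. It can exceed 20 if the excursion also shrinks. The percentages rest on assumed curves and do not predict bias in this trial.

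The consequence is modest. The OGTT is exploratory, the primary endpoint is adverse events, and no stated decision depends on OGTT AUC. The conflict over the OGTT baseline day can be read directly in the documents and needs correcting in any case.

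**What to change.** In Protocol 10.3.3.1 and SAP 9.4.1–9.4.2:

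- Keep total AUC(0-2h), described as total post-load exposure.
- Add net incremental AUC(0-2h) = total AUC − 2 h × same-day pre-load concentration, for glucose and insulin at both OGTTs.
- Analyse both measures by regimen against placebo, with the Day -1 OGTT value of the same measure as a stated covariate. At present the covariate is optional, and the SAP's non-repeated example code omits it. Report the two measures side by side.
- Limit statements about the excursion, or the insulin response above fasting, to the incremental measure.
- Name one OGTT baseline. SAP 9.4.1 should agree with the schedule, where the pre-treatment OGTT is on Day -1, and any departure from the protocol should be listed in SAP Section 11.

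The cost is one derived variable per analyte and one more table, with no new samples. The downside is that incremental AUC is noisier and can rise when only fasting glucose falls, so the text should say that it is read together with total AUC.
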